Protocol Title:

Comparison of Timing of Initiation on the Efficacy of Gabapentin in Treating
Neuropathic Pain in Spinal Cord Injury (SCI).

2/4/20

ClinicalTrials.gov Identifier: NCT04256603

Introduction:

Neuropathic pain is a common complaint in those with spinal cord injury (SCI) that has a significant negative effect on quality of life. This makes the treatment of neuropathic pain a priority in the SCI population. Efficacy of various treatments, however, remains controversial. There is evidence to support that gabapentin and pregabalin have some benefit in reducing neuropathic pain (1). Other positive effects of gabapentin on those with SCI have also been demonstrated. However, there has not been a study on the influence of timing of initiation of gabapentin on the efficacy of using it to treat neuropathic pain in the SCI population. Such a finding could change the standard of care in treatment of acute SCI.

The pooled prevalence of neuropathic pain post spinal cord injury is 53% (2). Not only common, neuropathic pain is pervasive, affecting aspects of patients' lives including sleep, physical function, and mood that in turn impact their activities—work and recreational alike (3). Thus, neuropathic pain management contributes to quality of life for a majority of people with SCI.

Although a high priority, the treatment of neuropathic pain in SCI remains notoriously difficult (4). Treatment options may be divided into pharmacologic and non-pharmacologic. Pharmacologic agents studied include amitriptyline, gabapentin, pregabalin, opiates, lidocaine, ketamine, valproate, lamotrigine, levetiracetam and carbamazepine; the most studied of which are amitriptyline, gabapentin, and pregabalin (5).

Gabapentin's potential is not limited to neuropathic pain management, making it a particularly compelling treatment option in the population with acute SCI. Gabapentin leads to improvement in total motor scores (6-9), reduced spasticity, reduced autonomic dysreflexia, and improved mood (8, 9). Animal models suggest it may be neuroprotective in the acute phase of injury (10). In those who undergo spine surgery, regardless of presence of SCI, gabapentin given perioperatively leads to reduced opiate use and decreased pain in post-operative period (11). Additionally, when compared to narcotic alternatives, gabapentin has minimal side effects.

Neuropathic pain in SCI is common, impactful, and difficult to treat. Gabapentin is effective in the management of symptoms and concerns related to SCI including motor recovery, spasticity, and mood among others. This makes gabapentin an important pharmacologic intervention, which compels providers to define treatment guidelines related to its use. One aspect of which should relate to the timing of initiation of therapy. The goal of this study is to determine whether early initiation of treatment with gabapentin will decrease average pain scores and opiate use when compared to late initiation of treatment with gabapentin in the population with acute SCI. Gabapentin, although used commonly, is not started in all patients with acute SCI but is often started at the onset of neuropathic pain. If gabapentin is found to be more effective when initiated early, it would be reasonable to start gabapentin immediately following acute SCI in all patients in whom it is not otherwise contraindicated.

1. Objectives

- Primary

- To determine if the time from injury influences the prevalence of neuropathic pain in acute SCI
- To determine if the use of gabapentin in the early acute period influences the prevalence of neuropathic pain in patients with acute SCI
- To compare the efficacy of acute versus subacute initiation of gabapentin in treating neuropathic pain in SCI

- Secondary

- To compare the overall pain scores
- To determine the prevalence of neuropathic pain in those with SCI at admission and discharge to the inpatient rehabilitation hospital
- To compare the use of opiates
- To compare the average daily change in Functional Independence Measure (FIM)
- To compare the change in total motor score on the ASIA impairment scale
- To identify side effects of treatment with gabapentin and their frequency

2. Endpoints

Primary

- Presence of neuropathic pain at time of enrollment and again around time of discharge (Douleur Neuropathique 4, DN4)
- Neuropathic pain level (Neuropathic Pain Scale, NPS) at time of enrollment and again around time of discharge

Secondary

- Average pain level recorded in nursing flowsheet (Numeric Pain Rating Scale, NPRS)
- Weekly total use of opiates (total morphine milligram equivalents, MME)
- Change in FIM during rehabilitation
- Change in total motor score on the ASIA impairment scale during entire rehabilitation course
- Side effects attributed directly to gabapentin in physician documentation and whether or not gabapentin was stopped due to these side effects

3. Design

- Prospective, observational, cohort, single center study
- The study will enroll subjects with acute spinal cord injury who are admitted to acute inpatient rehabilitation at MetroHealth Rehabilitation Institute (MRI).

- After enrollment, subjects will be followed through the end of their acute rehabilitation stay including any interruption in rehabilitation for which they require ED evaluation and/or acute hospital readmission so long as they return to MRI.
- Around the time of enrollment, subjects will be asked to complete the DN4 questionnaire and the NPS.
- Around the time of discharge, subjects will be asked to complete a second DN4 questionnaire and the NPS.
- The remainder of the data collection will be through review of the patient's electronic medical record (EMR).
- Patients will be divided into those who first received gabapentin during their acute inpatient hospitalization, prior to admission to acute rehabilitation, and those who did not. Additionally, the timing of gabapentin initiation will also be recorded.

4. Subject selection

- Study population

Subjects are patients who suffered acute spinal cord injury for which they are admitted to acute inpatient rehabilitation at MRI.
- Inclusion criteria

Subjects who meet all the following criteria may be given consideration for inclusion in this clinical investigation, provided no exclusion criterion is met

 1. Clinical diagnosis of acute spinal cord injury
 2. Admission to MRI for acute inpatient rehabilitation
- Exclusion criteria

Subjects who meet one or more of the following criteria will be excluded from this clinical study.

 1. Unable to communicate verbally or by writing, unable to follow basic instructions, or unable to answer questions regarding their symptoms

5. Subject Accountability

- Point of enrollment

The point of enrollment is the time at which time a subject signs and dates the valid, IRB approved informed consent form. No study-related procedure or assessments can take place until the informed consent form is signed.
- Withdrawal

All subjects enrolled to the study (including withdrawal or lost to follow-up) shall be accounted for and documented.

Reasons for withdrawal include:

 1. Physician discretion
 2. Subject choice
 3. Lost to follow up
 4. Death

Subjects may withdraw from the study at any time, with or without reason without prejudice to further treatment.

6. Study methods

- Pre-screening

To determine eligibility for enrollment into the study, the inclusion and exclusion criteria must be assessed.

- Informed consent

After a patient has been identified as a potential candidate, based on meeting all inclusion and no exclusion criteria, written Informed Consent must be obtained by asking patients to read and review the valid IRB-approved Informed Consent. The informed consent process will abide by the MetroHealth Medical Center IRB process.

- Initial Visit

The initial visit will occur at or within 7 days of the time of enrollment and admission to rehabilitation

- o Visit Type: Visit to patient while they are admitted to hospital
 - Admission DN4 and NPS

- Final Visit

The final visit will occur at or within 7 days of the time of discharge from MRI

- o Visit Type: Visit to patient while they are admitted to hospital
 - Discharge DN4 and NPS

- Additional data collection: As outlined in Figure 2

The data collection will be completed via review of the EMR of each subject, and will include the following:

- o Demographics
 - Age
 - Sex
 - Race
 - History of drug use
 - History of smoking
- o Home pain medications prior to SCI injury
- o Date of injury
- o ASIA impairment scores (AIS; 1st documented AIS, rehabilitation admission AIS, and rehabilitation discharge AIS)
- o Operative vs nonoperative management of SCI
- o Length of stay in rehabilitation
- o Rehabilitation admission and discharge FIM scores
- o Rehabilitation admission and discharge total motor scores (TMS) as recorded on AIS
- o Pain scores (NPRS)
 - Average score per week from injury as documented in EMR
- o Opiate use
 - Total weekly MME per week from injury

- Side effects
 - Record side effects attributed to gabapentin by treating physician
 - Record if therapy was stopped and why (ineffective, no longer required, adverse reaction)

7. Statistical Analysis Plan

Subject demographics will be summarized by typical descriptive statistics to compare means or medians and measures of variability

The relationship between the presence of neuropathic pain and: 1) the time from injury; 2) the timing of gabapentin initiation will be evaluated by building logistic regression models with dichotomous neuropathic pain (measured by DN4) as the dependent variable and time as the independent variable. Potential confounding variables will be added to the model if independently associated with the outcome of interest or based on theoretical grounds.

The efficacy of gabapentin by timing of initiation will be analyzed with a regression model with change in pain on the Neuropathic Pain Scale from admission to discharge with timing of gabapentin initiation as the independent variable. Potential confounding variables will be added to the model if independently associated with the outcome of interest or based on theoretical grounds.

8. Data analysis

- All enrolled subjects will be eligible for evaluation.

9. Data Safety/ Monitoring

The PI and co-investigators will monitor the progress of the research study, including assessments of data quality, participant recruitment, accrual and retention, subject's confidentiality, any adverse event(s), and external factors or relevant information that might have an impact on the safety or ethics of the study.

After recruitment, data analysis will occur and any changes to the risk/benefit ratio to study participation will be identified and reported to the IRB. In addition, the PI and co-investigators will meet on an annual basis and reports of the meeting will be submitted to the IRB.

If an adverse event occurs, it will be reported immediately to the MetroHealth Institutional Review Board (IRB). If an unexpected adverse event occurs, the investigators will assess the risk/benefit ratio of the study and submit any modifications deemed necessary to the IRB for approval. At the time of the IRB renewal, the PI will

submit information about the frequency of the monitoring, the dates that the monthly meeting took place, a summary of the cumulative adverse events, external factors or relevant information that might have an impact on the safety or the ethics of the study, and final conclusions regarding changes to the anticipated risk/benefit ratio to study participation and final recommendation related to the continuation, changing, or termination of the study.

10. Study Assessments

1. Assessment of presence of neuropathic pain (DN4) at time of admission and discharge
2. Neuropathic pain levels (Neuropathic Pain Scale, NPS) at time of admission and discharge
3. Pain scores (NPRS)
4. Change in pain scores
5. Opiate use (MME)
6. Change in opiate use
7. Average daily change in FIM (calculated [discharge FIM – admission FIM]/LOS)
8. Change in TMS on the ASIA impairment scale during entire rehabilitation course
9. Adverse events

Adverse events will be noted including documented reports of side effects and whether or not drug was stopped due to adverse effects.

11. Amendments

- If a protocol revision is necessary which affects the rights, safety or welfare of the subjects or scientific integrity of the data, an amendment is required.
- Appropriate approvals (IRB) of the revised protocol must be obtained prior to implementation.

12. Deviations

- No changes or deviations from this protocol, except to protect the life and physical well-being of a subject in an emergency will be made.
-

13. Potential risk and benefits

- All the risks are related to the completion of questionnaires and storage of PHI (see Procedure Consent Form).
- The benefits are all related to the future implications of the study on clinical practice and participation will not impact the subjects directly.

14. Informed consent

- Subject participation in this study is voluntary. Informed consent is required from all subjects\.
- The process of obtaining Informed Consent will follow MetroHealth/IRB process
- Refer to Consent Form

15. Bibliography

1. Guy, S., et al. "Anticonvulsant medication use for the management of pain following spinal cord injury: systematic review and effectiveness analysis." *Spinal Cord*, vol. 52, no. 2, 2014, pp 89-96.
2. Burke, D., et al. "Neuropathic pain prevalence following spinal cord injury: A systematic review and meta-analysis." *European Journal of Pain*, vol. 21, no. 1, 2017, pp 29-44.
3. Siddall P.J. & Middleton J.W. "Spinal cord injury-induced pain: mechanisms and treatments." *Pain Management*, vol. 5, no. 6, 2015, pp 493-507.
4. Kramer J.L., et al. "Neuropathic pain following traumatic spinal cord injury: Models, measurement, and mechanisms." *Journal of Neuroscience Research*, vol. 95, no. 6, 2017, pp 1295-1306.
5. Hagen, E. M. & Rekand, T. "Management of Neuropathic Pain Associated with Spinal Cord Injury." *Pain Therapy*, vol. 4, no. 1, 2015, pp 51-65.

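### The primary DN4 endpoint does not separate neuropathic pain that predates the injury from pain that followed it, which can dilute the timing comparison or bias it in either direction

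*Combined protocol and SAP*

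**What the plan says.** Section 1 (Objectives) lists three primary aims. The first is about time: "To determine if the time from injury influences the prevalence of neuropathic pain in acute SCI". The second turns to early treatment and reads "To determine if the use of gabapentin in the early acute period influences the prevalence of neuropathic pain in patients with acute SCI". The third, on timing of treatment, is "To compare the efficacy of acute versus subacute initiation of gabapentin in treating neuropathic pain in SCI".

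Section 2 (Endpoints) measures these with two instruments. One is "Presence of neuropathic pain at time of enrollment and again around time of discharge (Douleur Neuropathique 4, DN4"). The other is "Neuropathic pain level (Neuropathic Pain Scale, NPS) at time of enrollment and again around time of discharge". Neither definition mentions onset, site, cause or an index pain.

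Section 4 (Subject selection) has one exclusion: "Unable to communicate verbally or by writing, unable to follow basic instructions, or unable to answer questions regarding their symptoms". Section 6 (Study methods) gives the content of the first visit as "Admission DN4 and NPS", and the discharge visit repeats the same two instruments. The chart-review list in Section 6 includes the date of injury and "Home pain medications prior to SCI injury". It has no item for earlier neuropathic pain, for when a pain began or for where it is.

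Section 7 (Statistical Analysis Plan) uses logistic regression for DN4 status and a regression on NPS change. Confounders may enter either model if they are associated with the outcome or can be justified on theory; none is named. Section 8 allows every enrolled subject to be evaluated.

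**The concern.** A patient who had a painful neuropathy or radiculopathy before the injury can be enrolled. If that pain scores DN4-positive, the patient counts as an outcome event in a model that asks whether time since injury, or early gabapentin, changed the outcome. For that pain neither could have done so.

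Two features of the design make it unsafe to assume that such patients are balanced between groups. Treatment is not randomised; Section 3 (Design) describes an observational cohort, and the Introduction says that gabapentin is often begun when neuropathic pain appears. Patients with an older neuropathic pain may therefore be started on it sooner. Against that, Section 3 defines the early group by a first receipt of gabapentin in the acute hospital. Read literally, someone already taking it at home did not first receive it there and joins the comparison group. The two mechanisms push in opposite directions.

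The Introduction says that a favourable result could support starting gabapentin straight after injury in all patients without a contraindication. A bias of unknown sign in a primary endpoint matters for such a conclusion.

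A smaller, related gap concerns NPS change. Nothing records whether the discharge rating refers to the pain rated at admission, so a reader cannot tell persistence of one pain from replacement by another.

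**Working it through.** The plan gives no sample size, power, effect size or standard deviation, so it has no figure of its own to reproduce. The check has two parts.

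**1. Can the plan identify pre-injury pain?** Taking the places in turn:
- Endpoint definition (Section 2): no onset or site condition.
- Eligibility (Section 4): prior neuropathic pain is not excluded.
- Visits (Section 6): DN4 and NPS only.
- Chart review (Section 6): injury date, but no pain-onset date to set against it. Home pain medications miss untreated neuropathy and do not separate neuropathic from other pain.
- Models (Section 7): the confounder rule can use only what is recorded.

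The visible text therefore offers a proxy and no direct item.

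**2. What could it do to the DN4 comparison?** Let p be the prevalence of SCI-related neuropathic pain in a group and q the share with pre-injury neuropathic pain. Assume that the two are independent and that pre-injury pain always scores DN4-positive. Then

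observed prevalence = p + (1 − p) × q.

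Assumed values: p = 46% early and 60% other. Their midpoint, (46 + 60)/2 = 53%, equals the pooled prevalence in the Introduction. All values of q are assumed, since the documents give none.

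| q early | q other | Observed early | Observed other | Difference, other minus early |
|---|---|---|---|---|
| 0% | 0% | 46.0% | 60.0% | 14.0 points |
| 10% | 10% | 0.46 + 0.54 × 0.10 = 51.4% | 0.60 + 0.40 × 0.10 = 64.0% | 12.6 points |
| 20% | 5% | 0.46 + 0.54 × 0.20 = 56.8% | 0.60 + 0.40 × 0.05 = 62.0% | 5.2 points |
| 5% | 20% | 0.46 + 0.54 × 0.05 = 48.7% | 0.60 + 0.40 × 0.20 = 68.0% | 19.3 points |

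With equal q the true difference is multiplied by (1 − q): 14.0 × 0.90 = 12.6.

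*No true effect.* Put p = 53% in both groups. A share of 20% gives 0.20 + 0.80 × 0.53 = 62.4%, and a share of 5% gives 0.05 + 0.95 × 0.53 = 55.35%. The gap of 7.05 points (odds ratio 1.34) is spurious. It reads as harm if the early group has the larger share, and as benefit if the other group has it.

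*Cost of dilution alone.* Take 53% against an assumed 38%, with assumed two-sided alpha 0.05, power 80% and equal groups. The number needed per group is 172 at q = 0, 215 at q = 10% and 267 at q = 20%; the observed differences are 15.0, 13.5 and 12.0 points.

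The effect on NPS change cannot be quantified, because the documents give neither a standard deviation nor an effect size.

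**The case against.** The strongest reply is that the objectives speak of neuropathic pain in people with acute SCI, not of pain caused by the injury. On that wording, all-cause DN4 prevalence is a legitimate target. This stands in part: the endpoint does not contradict the objectives, although the Introduction frames the problem as pain after spinal cord injury. What remains is that objectives 1 and 2 ask about influence, and pre-injury pain is not open to the influences studied.

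Second, home pain medications and the confounder rule give a partial route to adjustment. That is true, but the proxy is indirect, is not a named covariate and leaves the scoring of DN4 unchanged.

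Third, the absence cannot be fully verified. Figure 2 is not shown, and neither are the DN4 and NPS forms and their instructions. This stands as a limit on the point.

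Fourth, the magnitudes rest on assumed shares, and treated or mild old pain may score DN4-negative. This also stands. A lower chance of scoring positive acts like a smaller q and shrinks every shift shown.

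A reader might infer that NPS change is invalid unless it is confined to the pain rated at admission. The documents do not support that. If the target is overall neuropathic pain, no change is a correct result when one pain replaces another of equal severity. Confining the score would also drop new pain and leave patients without admission pain with nothing to re-rate.

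**Conclusion.** The point holds for the DN4 endpoint: as far as the visible text shows, the plan neither excludes nor records neuropathic pain that predates the injury, and it analyses such pain as an outcome that exposure could have changed. It is a gap in a design choice that should be closed, not an internal contradiction.

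A reader might infer that the bias always runs toward no effect, or that early use would always look worse. Neither follows. Equal shares dilute, but the group definition in Section 3 and the lack of randomisation allow unequal shares in either direction. With the assumed shares, an assumed true difference of 14.0 points could appear as anything from 5.2 to 19.3. These figures show direction and range only. They rest on assumed prevalences, independence, and every pre-injury pain scoring DN4-positive; the actual share is unknown. For NPS change the gap is one of interpretation, and its size is not known.

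**What to change.** - **Collect.** At the two planned visits, ask for each reported pain whether it began before the injury and where it lies relative to the level of injury.
- **DN4.** Analyse DN4-positive pain with onset after the injury alongside any-onset DN4, and state in advance which is primary.
- **Models.** Name pre-injury neuropathic pain as a covariate in the DN4 and NPS models.
- **NPS.** Keep the change score as overall neuropathic pain at both visits. Record at discharge whether the rating refers to the same pain as at admission, and add a sensitivity analysis limited to subjects who rated the same pain.
- **Figure 2.** If it or the forms already contain onset or site items, bring them into the text and the analysis.

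The cost is a few questions at visits already scheduled, plus endpoint and model wording. Onset is self-reported, the visits become slightly longer (a subject with both old and new pain needs DN4 scored for each), and the counted prevalence may fall slightly. Treatment is not affected.

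### The weekly opiate total has no rule for the incomplete discharge week, so constant daily use can appear as a fall in opiate use

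*Combined protocol and SAP*

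**What the plan says.** The opiate endpoint in section 2 (Secondary) is "Weekly total use of opiates (total morphine milligram equivalents, MME". Section 6, under additional data collection, gives the item as "Total weekly MME per week from injury", so each value is a sum over a seven-day block that starts at injury. Section 10 then lists "Change in opiate use" as an assessment, without a formula, a first week or a last week.

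Under section 3, "subjects will be followed through the end of their acute rehabilitation stay", with interruptions for emergency evaluation or acute readmission included if the patient returns. Discharge is therefore the end of observation, and nothing ties it to the end of an injury week.

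Two other secondary measures are already scaled. The pain rating is "Average score per week from injury as documented in EMR", and function is "Average daily change in FIM (calculated [discharge FIM – admission FIM]/LOS". The opiate measure has no denominator. Section 7 specifies models for DN4 and for change in NPS, and none for MME.

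**The concern.** A sum over a fixed block is comparable between weeks only if each block is fully observed. The discharge week is complete only when discharge happens to close a seven-day block counted from injury. In every other case the total is low because days are missing, whether or not the patient took less opiate. A weekly average, as used for the pain score, is not lowered mechanically in this way.

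The Introduction names lower opiate use, beside lower pain scores, as what early gabapentin is hoped to achieve, although sections 1 and 2 place it among the secondary objectives and endpoints. The artefact imitates a fall in opiate use towards discharge, which is the direction a reader would take as improvement.

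**Working it through.** **Inputs.** The documents give no MME level, no length-of-stay distribution and no planned opiate comparison, so there is no figure of the plan's own to reproduce. The structure comes from sections 2, 3, 6 and 10: weekly sums, weeks from injury, observation to discharge. The following are assumptions: daily use is constant at m (true change zero), every week before the last is fully observed, and durations are as stated below. The percentages do not depend on m.

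**Notation.** D is days from injury to discharge, k = D/7 rounded up is the number of injury weeks, and r = D − 7(k − 1) is the number of days observed in the last week, from 1 to 7.

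**1. Last week against a full week.** The apparent change is r·m/(7·m) − 1 = r/7 − 1.

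| Days observed, r | 1 | 2 | 3 | 4 | 5 | 6 | 7 |
|---|---|---|---|---|---|---|---|
| Apparent change | −85.7% | −71.4% | −57.1% | −42.9% | −28.6% | −14.3% | 0% |

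If r is uniform on 1 to 7, its mean is 4 and the average change is 4/7 − 1 = −42.9%. At an illustrative 30 MME/day, a full week is 210 MME and the average last week is 120.

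**2. What drives it.** The result depends only on r, that is, on D modulo 7. D = 15, 29, 50 and 85 days all give −85.7%; D = 21 and 28 both give 0%. A longer stay does not make the last-week fall larger or smaller.

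**3. Noise.** With r uniform on 1 to 7, its variance is (49 − 1)/12 = 4, so its SD is 2 days. Discharge day alone therefore gives the last-week total an SD of 2/7 = 28.6% of a full week.

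**4. Mean weekly total over all weeks.** Averaged over r, the bias is [7(k − 1) + 4]/(7k) − 1 = −3/(7k).
- k = 3: −3/21 = −14.3%
- k = 6: −3/42 = −7.1%
- k = 8: −3/56 = −5.4%
- k = 12: −3/84 = −3.6%

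**5. Least-squares slope over weeks.** An average shortfall of 3m in the last of k weeks gives a slope of −18m/[k(k + 1)].
- m = 30: −540/12 = −45 MME per week for k = 3, and −540/72 = −7.5 for k = 8
- m = 50: −900/12 = −75 and −900/72 = −12.5

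**6. Two groups with identical daily use.** These come from simulation with normal durations, SD 10 days; the means are assumed.

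| Mean injury-to-discharge time | Last-week change | Bias in mean weekly total |
|---|---|---|
| 35 v 35 days | about −43% in both | −8.3% in both |
| 30 v 50 days | about −43% in both | −9.8% v −5.7% |

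The last-week fall is about the same in both groups even when durations differ. The bias in the mean differs, by about 4 percentage points, only when durations differ.

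**7. After dividing by observed days.** The last-week value is r·m/r = m for every r, so the artefact is zero.

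**The case against.** The strongest reply is that the plan never tells anyone to treat a short week as a full one. It names a weekly total and a change, leaves the change undefined and gives no MME analysis. An analyst might drop the discharge week or scale it. This stands to the extent that the artefact is conditional on using the week unscaled. But unscaled is how the endpoint is written, and scaling it would depart from the stated measure.

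The direction could also be questioned. If only rehabilitation days were counted, the admission week would be cut too, and the two shortfalls would offset on average. That is possible because the change is undefined. However, section 6 counts weeks from injury, and even with an offset on average, single patients' changes would still vary with their admission and discharge days.

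Three stronger readings are tempting and are not supported:
- A reader might infer that the false fall grows or shrinks with length of stay. The last-week fall does not (step 2). Total duration matters only for means or slopes across weeks, and then it is injury-to-discharge time that counts, not the rehabilitation stay alone.
- A reader might infer a known bias between early and late starters, for instance the 14.3 − 5.4 = 8.9 points between 3 and 8 weeks. The documents give no durations by group. The assumed 30 v 50 days gives about 4 points, and equal durations give none.
- A reader might extend the problem to weeks with an acute readmission. Section 3 keeps those days in follow-up, and nothing says their medication data are missing.

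Using only complete weeks would also remove the artefact, at the price of discarding up to six days before discharge. So a per-day rate is the better remedy but not the only valid one.

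**Conclusion.** The concern holds in a limited form. The opiate endpoint is an unscaled sum on an injury clock, observation ends at discharge, and there is no rule for incomplete weeks. Used as written with constant daily use, the discharge week reads 0% to 86% low, and 43% low on average if the discharge day is uniform over the week. The section 10 change measure can therefore show a fall that did not occur. That it will do so is not established, because the weeks to be compared are not named.

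Means and slopes across weeks are biased more for shorter courses. The group comparison is biased only if early and late starters differ in injury-to-discharge time or in discharge timing. In an observational cohort grouped by when gabapentin began, equality cannot be assumed, but neither is a difference documented. Without one, the damage is a distorted within-patient change and extra noise. The MME levels and durations used are illustrative. The point concerns a secondary endpoint and leaves DN4 and NPS untouched, but it should be corrected because the remedy is small and opiate use is part of the study's stated goal.

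**What to change.** In sections 2, 6 and 10, define opiate use as mean daily MME in each week from injury: MME given in that week divided by the number of days in that week with EMR medication data. Days with medication data and no opiate given count in the denominator. Calculate the change in opiate use on this scale, and name the two weeks, or the summary over weeks, that it compares.

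The cost is one line in each of the three sections and a count of observed days per week, taken from the same EMR review. The plan already records "Date of injury" and "Length of stay in rehabilitation".
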